8	Send mass mailing to identify interested providers	6-10			X			
9	Enroll/randomize providers (Intervention Time 0 (I0))	6-10			X	X		
10	Collect baseline practice data online	7-23					X	
11	Complete practice run-in phase data (exit cards)	7-23					X	
12	Send repeated emails to dentist/hygienist for retention	7-23			X		X	X
13	Collect usage data from websites	7-23	X		X		X	X
14	Have practice enroll patients through Refer2Quit	7-23			X	X		
15	Send provider reports of patient enrollment	7-23				X	X	
16	Measure Referral Rates at baseline, 6 and 12 months after practice enrollment using patient exit card surveys (first cards collected in run-in phase)	7-12					X	H1
17	Measure number of referrals using Refer2Quit and Information prescriptions	7-23						H1
18	Measure rates of patients who GO to Decide2Quit	7-23					X	H2
19	Measure patient QUIT rates, quit attempts, and readiness to quit at 6 months (telephone follow-up)	10-30						H3
20	Validate 6-month quit with Cotinine*	10-30					X	H3
21	Test Hypotheses, prepare manuscripts	10-36						X

\*Mailed salivary cotinine (Salimetrics); H1 = Hypothesis1; H2 = Hypothesis 2; H3 = Hypothesis 3 (See D5 for details of Measures)

To further clarify the flow of the development, intervention, and evaluation, Figure 3 below summarizes the planned timeline for accomplishing key tasks.

[figure not shown]

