Outcome Expectation - Counseling			B,F			
Patient contact (hours/week)	B		B,F			
How Busy is Practice?		B,F				
Practice Location		B				
Perceived Barriers to Counseling			B			
Use of HI-QUIT (Providers)			F			
Pre-intervention tobacco counseling				B		
Post-intervention Refer				H1		
Use of website (Patients)					H2	
Type of Tobacco Use				B	B	F
Patient demographics					B	F
Level of Addiction					B	F
Medical Comorbidities					B	F
Past Quit History					B	F
Readiness to Quit				H3		H3
Quit Attempts						H3
Tobacco Prolonged Cessation*						H3

B= baseline covariate, F = Follow-up; H1= Outcome for Hypothesis 1; H2= Outcome for Hypothesis 2; H3= Outcome for Hypothesis 3; \*validated by cotinine

Principal Investigator/Program Director (Last, First, Middle): DPBRN c/o [name]

target content of the website to individual patients and as covariates in our analysis of cessation rates of those who participate in the website (H2). Using tracking data, we will also create variables related to participation similar to those of providers described above.

**5) Patient follow-up assessment (Hypothesis 3)** – Tobacco cessation behaviors will be assessed by follow-up telephone interviews at six months from website enrollment. We will have three measures of tobacco cessation behavior: 1) Tobacco cessation, 2) Quit Attempts, and 3) Stage of Change (Transtheoretical Model). As recommended in the new standard criteria for evaluation smoking cessation trials, smoking cessation will be validated at six months using cotinine. We have had experience in previous studies in validating cessation by using mailed salivary cotinine measures. Currently, we are using Salimetric’s mailed salivary cotinine test.

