**D8. Main Evaluation Measures**

As depicted in Figure 4, HI-QUIT is designed to have a sequence of effects on the process of care within each clinical microsystem. Thus, we have designed our main evaluation to assess several key areas of influence that we have abbreviated as **Refer -> GO -> QUIT**. For our hypotheses, we have three primary dependent variables. Each of the outcomes is collected at the patient level and is used to create a proportion. The first link in the chain of evaluation is of course to assess the performance of the provider. We will use the exit cards to assess the proportion of smokers who are referred. This is assessed at discrete time points (Patients recruited in 3 cohorts at intervention Time 0 (I0) (pre-intervention), I0 + 6 months, I0 + 12 months,).

This analysis is solely to assess provider performance and data are collected from patients anonymously. The proportion of smokers who are referred who GO to the website (H2), and the subsequent

Table 10: Dependent (outcome) variables (Refer -> GO -> QUIT)					
Label	Question	Source	Collected	Numerator	Denominator
Refer (H1)	During your provider’s visit TODAY did anyone: Refer you to Decide2Quit* - a website with information about tobacco?	Patient Exit Card	Discrete Intervals (baseline, 6 and 12 Months)	Number Referred	Number of Smokers
GO (H2)	Proportion of patients from the practice who log onto website	Website tracking and information prescriptions	Continuous	Number who GO	Number Referred ‡
QUIT (H3)	Do you currently smoke cigarettes (smoked even 1 puff in the last 7 days)?	6 month survey†	Continuous	Number who QUIT	Number Referred ‡
* control website for Controls; † validated using mailed cotinine saliva kit. ‡ Assessed by web tracking in intervention, in control by leave-behind receipts from information prescriptions					

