Cotinine biochemical verification: In 2002, the SRNT Subcommittee on Biochemical Verification published recommendations and evidence to aid the decision-making in choosing biochemical verification. This article divided studies into clinic-based trials (usually with less than 500 participants) where misclassification is higher and the need for biochemical verification is high and participation in biochemical verification is also high, versus population-based studies where misclassification is low and biochemical verification is less needed, and is in fact less feasible (with non-response rates up to 70%). In planning the study, we feel that HI-QUIT is closer to a clinic-based trial. The connection to the clinical microsystem makes this study more intense than public health interventions and may change the demand characteristics. To increase participation rates for the mailed salivary cotinine, we will provide an additional incentive of \$50 for completing this sample. However, we acknowledge that not all patients may complete cotinine validation by mail. For patients who self-report quitting at six months, but fail to return their cotinine saliva sample, we will use their self-report data, acknowledging that those who do not return their cotinine sample will be more likely to mis-report cessation. We will carefully assess for differential misclassification comparing intervention and control. First, we will compare participation rates for returning the cotinine sample by intervention and control. Next, we will assess self reported cessation among those that do and do not return the cotinine sample (comparing intervention and control). Finally, we will compare the misclassification rates among those that did return the sample (again intervention vs. control). If differences are detected, this would represent a case of non-ignorable missing data. Using these rates, we will conduct sensitivity analyses to assess the impact of differences in participation and misclassification on our main outcome and use pattern mixture approaches to assess how much our main analysis might change.

**D9. Analysis Plan:** For each practice, HI-QUIT is available for 20 months (see Figure 3, section D1). We plan to assess the impact of the intervention throughout this interval.

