We will approach this analysis in two ways. In both approaches, the numerator will be the number of patients who report cessation at six-month follow-up calls. In our primary analysis, we will use an intent-to-treat analysis in that we will include all practices (regardless of whether they actually use the intervention) and will include all smokers who are referred (the same denominator used in H1) regardless of whether they GO to the website. This represents a conservative assessment since we assume that many patients will not GO, and for the purposes of analyses, we will assume that these patients will not have quit. The most conservative analysis would be to use the total number of smokers seen in the practices as the denominator. However, we will not know this number exactly. Our exit cards give an estimate but we do not have a continuous measure of total smokers.

As a secondary analysis, we will assign the denominator as the number of patients who GO to the website. For this secondary analysis, consistent with current guidelines for smoking cessation trials, we will assume that patients who are lost to follow-up, including those who GO and do not agree to follow-up, are smokers.

We have assumed a control cessation rate of 17% among those with completed cases (follow-up complete) in the control group based on a range of completed case and intent-to-treat evaluations of prior internet smoking cessation interventions (Table 11). For the purposes of power calculations, we estimate

**Table 11:** Six-month cessation anticipated among completed cases, those who go to the website, and those referred from 80 practices.

	Six-month cessation among Completed Cases*†		Cessation among those who GO		Cessation among those who are referred‡ (Primary Analysis)	
	n/N	Proportion	n/N	Proportion	n/N	Proportion
Intervention	120/456	26%	120/760	16%	120/1920	6%
Control	20/120	17%	20/200	10%	20/960	2%

\* Completed Cases are those with completed six-month telephone surveys  
 † Assumes 60% follow-up among those who GO (see Table 8 for number who go per practice) and assigns not abstinent to those without follow-up  
 ‡ Assumes those who are referred and do not go are **not abstinent**, based on estimates of those referred from Table 8 multiplied by the number of practices

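### D9 counts every self-reported quit in the H3 numerator, although D7, the task list and Table 10 call the quit cotinine-validated; how to score a returned sample that contradicts the report is not stated

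*Protocol*

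**What the plan says.** **Validated cessation.** D7, item 5 (patient follow-up assessment), says that "smoking cessation will be validated at six months using cotinine". In D8, the QUIT row of Table 10 names the six-month survey as its source, with the footnote "validated using mailed cotinine saliva kit". The task list (Table 6) has "Validate 6-month quit with Cotinine" as an H3 item.

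**A mixed rule.** The cotinine paragraph of D8 covers patients who report quitting "but fail to return their cotinine saliva sample, we will use their self-report data". It then plans three comparisons between arms: sample return, self-reported cessation in returners and non-returners, and misclassification among returners. If the arms differ, D8 treats this as non-ignorable missingness, and "we will conduct sensitivity analyses to assess the impact of differences in participation and misclassification on our main outcome", with pattern-mixture approaches.

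**Self-report.** D9, under the data definitions for H3, bases the outcome on the seven-day smoking question and adds: "In both approaches, the numerator will be the number of patients who report cessation at six-month follow-up calls". The two approaches are the primary analysis (all referred smokers) and the secondary one (those who GO). The H3 text of D9 does not mention cotinine.

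**The concern.** Take a patient who says at the six-month call that they have quit and then mails a sample showing active smoking. An analyst who follows D9 counts a quit. An analyst who follows Table 10 and takes D8's exception for unreturned samples as the only exception does not. The same data then give two H3 results, and the choice could be made after the results are known.

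D8 itself argues that the check matters. It places the trial nearer to the clinic-based type, where misclassification and the need for verification are higher, and says the link to the practice may change demand characteristics. The samples are collected with a $50 incentive and written consent. Under D9's numerator they change neither the primary nor the secondary H3 estimate.

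**Working it through.** **1. The scoring rule, case by case**

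| Patient who reports a quit | D9 as written | D7, D8 and Table 10 |
|---|---|---|
| Sample returned, confirms | Quit | Quit |
| Sample not returned | Quit | Quit (D8 states this) |
| Sample returned, contradicts | Quit | Not stated; implied not a quit |

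Only the third row is in dispute. Table 9 blurs it further: its cotinine mark sits on prolonged cessation, whereas D8 and D9 make point prevalence the H3 outcome.

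**2. The plan's own figures**

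Table 11, among those referred:
- Intervention: 120/1920 = 6.25%.
- Control: 20/960 = 2.08%.
- Difference: 4.17 points; ratio 3.0.

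D10 reaches the rounded 6% and 2% as 0.40 × 0.15 and 0.20 × 0.10.

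**3. Effect of the scoring rule**

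Let f be the share of reported quits that a test would disprove and r the share of samples returned. Scoring disproved reports as smokers multiplies each arm's quits by (1 − f × r). The protocol gives neither f nor r, so all values below are assumptions. The 30% return is an illustrative low value, prompted by D8's mention, for population-based studies, of "non-response rates up to 70" per cent.

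| Assumed f (intervention / control) | r | Intervention | Control | Difference (points) |
|---|---|---|---|---|
| 20% / 20% | 100% | 96/1920 = 5.00% | 16/960 = 1.67% | 3.33 |
| 30% / 10% | 100% | 84/1920 = 4.38% | 18/960 = 1.88% | 2.50 |
| 20% / 20% | 30% | 112.8/1920 = 5.88% | 18.8/960 = 1.96% | 3.92 |
| 30% / 10% | 30% | 109.2/1920 = 5.69% | 19.4/960 = 2.02% | 3.67 |

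The drop from 4.17 points is 0.83 or 1.67 with full return, and 0.25 or 0.50 with 30% return. With equal f and equal r, the ratio stays at 3.0. The formula takes non-returners to misreport as often as returners. D8 expects them to misreport more, so fewer false reports would be caught than shown.

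**4. Power**

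Inputs are D10's ICC of 0.017, 24 and 48 referrals per practice, 6% v 2%, and a two-sided chi-square test at 0.05. Design factors are 1 + 23 × 0.017 = 1.391 and 1 + 47 × 0.017 = 1.799, so the effective sizes are 17.25 and 26.68 per practice. D5 expects 30 to 40 practices per arm to complete follow-up.

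| Case | Rates | Power, 40 per arm | Power, 30 per arm |
|---|---|---|---|
| No disproved reports | 6% v 2% | 98.8% | 95.1% |
| 30% / 30%, full return | 4.2% v 1.4% | 93.3% | 84.3% |
| 30% / 10%, full return | 4.2% v 1.8% | 81.1% | 68.3% |
| 30% / 10%, 30% return | 5.46% v 1.94% | 96.9% | 90.7% |

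**5. Dependence of the corrected rule on return**

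Assume 20% misreport in both arms.
- Return 70% in intervention and 30% in control: 103.2/1920 − 18.8/960 = 5.38% − 1.96% = 3.42 points.
- Return 30% in intervention and 70% in control: 112.8/1920 − 17.2/960 = 5.88% − 1.79% = 4.08 points.

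Identical misreporting gives different estimates because return differs by arm.

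**The case against.** **D9's sentence is about denominators.** It introduces two denominators and says that the numerator is shared; the measure itself is defined in D8. This is a fair account of why the sentence was written. But the H3 text has no reference back to cotinine, and an analyst who follows it literally would not use the assay.

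**Validated need not mean counted only if confirmed.** D8 can be read as a self-report outcome with cotinine used to measure misclassification, and D8 and D9 then agree. This reading is open. A reader might infer that Table 10 and D8 settle the matter and exclude the disproved report; they do not, because the override is only implied. On the self-report reading, D7, the task list and Table 10 describe the outcome loosely, so a clarification is needed either way.

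**D8 already plans for differential misreport.** A reader might infer that over-reporting would pass unchecked into the H3 effect. It would not: D8's arm comparisons and pattern-mixture work are meant to detect and quantify it. Two limits remain. They do not re-score the numerator, and they are tied to a detected difference, so equal misreport in both arms would not trigger them.

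**The cut-off and discordant samples belong in the SAP.** The cut-off may well be there. The choice between self-reported and validated cessation is different, because this protocol already describes it in two ways.

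**Conclusion.** The point holds as an inconsistency in the definition of the H3 outcome. D9 as written scores a disproved report as a quit in both analyses, other sections call the quit cotinine-validated, and no section scores the discordant case.

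The size cannot be fixed from the protocol. Under the assumed disconfirmation rates, the planned 4.2 points becomes 3.3 or 2.5 with full return, and about 3.9 or 3.7 with 30% return. The larger drops need full return, which D8 does not expect.

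A reader might also infer that over-reporting is greater in the intervention arm. D8 says only that the practice link may alter demand characteristics and does not compare the arms. The 30% v 10% case is therefore an illustration of differential misreport, not a forecast. Equal misreport up to 30% leaves power at 84% or more even with 30 practices per arm. The main exposure is bias if misreport differs by arm, together with a primary result that depends on which section is followed.

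**What to change.** Amend D9 so that, in both the primary and the secondary H3 analysis, a quit is self-reported seven-day abstinence at six months that is not disconfirmed by a returned cotinine sample. Unreturned samples stay scored by self-report, as D8 states, and one cut-off is set in advance. Align D7, D8, Table 9 and Table 10 with this wording.

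Because the rule depends on sample return by arm, report two sensitivity analyses whether or not the arms are found to differ:
- the numerator by self-report alone;
- a version in which reported quits without a returned sample count as smokers.

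The second is severe when return is low. At 30% return and 20% disconfirmed in both arms, it gives 120 × 0.3 × 0.8 = 28.8/1920 = 1.5% v 20 × 0.3 × 0.8 = 4.8/960 = 0.5%. It should be read as a bound, alongside return by arm.

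The cost is a few sentences, two extra analyses and probably slightly lower reported quit rates. No new data are needed, since the samples are already planned.

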proportion who QUIT (H3) are assessed continuously throughout the study. For H2, the numerator is the number who GO, as tracked by HI-QUIT and the control website. The denominator is the number referred. Because of the nature of the Internet versus paper referral system, by definition, the continuous assessment of the number of patients who are referred is different by study arm. Our interest in H2 is the proportion of patients referred who logon, or ‘GO’, to the website (% who go = number who visit/number referred). In the intervention group, the webserver collects the number of patients entered into the system per practice (i.e.: denominator, the number referred). In the control group, patients are not entered into an electronic system, but are referred using an “information prescription.” In both groups, the intervention and control websites collect the number of patients who visit the site. Thus, assessment of the numerator is the same, but assessment of the denominator is systematically different by arm. We have developed protocol for more accurately measuring the denominator and the number referred in the control group by using the information prescription pads with a leave-behind notation of when the patient was referred. We will collect the empty prescription pads from the control practices to assess the number of patients referred for the denominator.

For H3, the dependent variable is point prevalent cessation (QUIT). Smoking cessation trialists have recommended assessment of smoking cessation in randomized trials using both measures of 1) point

Principal Investigator/Program Director (Last, First, Middle): DPBRN c/o [name]

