Secondary analysis: Our primary approach does have the potential for errors resulting from lost, damaged, or mis-used “information prescription” pads in the control. This would result in a differential misclassification in the control as compared to the intervention group. As much of this error would underestimate the control denominator, it would still provide a conservative estimate. However, it is true that the inherent difference in the intervention and control creates a difference in the assessment of the denominator. Thus, as a secondary analysis and as safeguard against these error sources, we will repeat the analysis using the number of patients who GO as the outcome, with careful adjustment for *patient volume, proportion of smokers, and rates of referral as assessed by the exit cards at discrete time points*. This will allow us to check for consistency of results. The secondary analysis for the number who GO will use linear regression to model the number of patients per practice who go to the website by treatment assignment adjusted as above, where the test of H2 will be the significance of the coefficient for treatment assignment.

**Hypothesis 3: The proportion of smokers who are referred who QUIT at six months will be larger among intervention compared with control because of the additional connectivity of HI-QUIT.**

Data Definitions for H3: The main dependent variable for H3 is the dichotomous outcome of patient tobacco cessation (quit). The primary independent variable is assignment to intervention or control group. We have designed a patient-level analysis around point prevalence cessation based on the following question: “Do you currently smoke cigarettes (smoked even 1 puff in the last 7 days)?”

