### **Qualitative Process Analysis – How Practice Characteristics Impact Use of the Referral System:**

Case-Comparison study - Our main analyses above are to test overall differences, Intervention versus Control. However, based on our prior experience, adoption of the intervention will vary. Some hygienists and practices will have high rates of referral and, despite our efforts, some practices may use Refer2Quit very little. Consistent with the framework for evaluation of complex interventions, we plan a second qualitative analysis to answer questions including: What organization and process factors are related to adoption, or not adoption, of the intervention? To accomplish this task, we plan to conduct semi-structured interviews with a random sample of providers.

The design is a case-comparison study, a subset of the multimethod assessment process (MAP).

Sample: We will use a selective sampling strategy. Selective sampling is defined as sampling subjects according to a preconceived, but reasonable initial set of criteria to obtain a broad array of informants. As the goal of our qualitative research is to obtain a range of opinions related to workflow processes, barriers, facilitators and other themes related to adoption, we will target specific practices and providers. Our first layer of selective sampling is to identify 1) high and 2) low-adopting practices. We also would like to obtain larger and smaller practice sizes. Thus, we will interview hygienists and dentists from an initial random sample of 8 high and 8 low-adopting practices among the 40 intervention practices (also split by large and small practice size).

Many qualitative research studies use a combination of selective sampling and theoretical sampling. We will conduct iterative analyses and may find that we do not reach theme saturation in some strata of our selective sampling after 16 practices. We have budgeted resources for up to 20 practices to provide for the needs of theoretic sampling and theme saturation.

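### The H3 primary analysis is labelled intent-to-treat across all practices, but its denominator is patients referred, so it is an analysis among referred patients

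*Protocol*

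**What the plan says.** Section D9 of the Protocol, under the data definitions for Hypothesis 3, describes the primary analysis in one sentence with two parts. The first is the label: "we will use an intent-to-treat analysis in that we will include all practices (regardless of whether they actually use the intervention". The second is the denominator: the analysis "will include all smokers who are referred (the same denominator used in H1) regardless of whether they GO to the website".

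Table 10 in D8 gives the number referred as the denominator for QUIT, and its footnote says how that number is obtained: "Assessed by web tracking in intervention, in control by leave-behind receipts from information prescriptions". The D8 text is more explicit for the intervention arm, where "the webserver collects the number of patients entered into the system per practice (i.e.: denominator, the number referred".

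D9 also considers a wider denominator: "The most conservative analysis would be to use the total number of smokers seen in the practices as the denominator". It sets this aside because the number is not known exactly: "Our exit cards give an estimate but we do not have a continuous measure of total smokers".

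The qualitative process analysis expects uneven adoption and says that "some practices may use Refer2Quit very little". In D5, the paragraph on attrition promises to keep the data of withdrawn practices for an intention-to-treat analysis.

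**The concern.** The two parts of the H3 sentence do not fit together. Under Table 10 a smoker enters H3 only after being entered in Refer2Quit or handed a prescription with a receipt. An intervention practice that does not use its system has no such smokers, so it adds nothing to either numerator or denominator of a patient-level analysis. Its inclusion is nominal.

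Referral happens after randomisation, and raising it is the purpose of the intervention. Conditioning on it gives up the protection that an intent-to-treat analysis is meant to provide. Two things are at stake:

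- A reader told that H3 is intent-to-treat over all practices would take it as the effect on cessation of assigning a practice to HI-QUIT. It estimates something else.
- The referred smokers may differ between arms. D9 itself expects that control practices may refer mainly those ready to change, while intervention practices refer less selectively.

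A smaller slip sits in the same sentence. It calls the referred smokers the denominator of H1, but in Table 10 the H1 denominator is the number of smokers, and the number referred is its numerator.

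**Working it through.** **Inputs from the protocol.** 40 practices per arm (Specific Aims). Per practice-year: 200 smokers, 48 (intervention) or 24 (control) referred, of whom 40% or 20% GO (Table 8 and D10). Quit rate among those who GO: 15% or 10% (D10). ICC for H3: 0.017 (D10).

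**The plan's own figures.**
- Referred: 40 × 48 = 1,920 and 40 × 24 = 960, the denominators of Table 11.
- Table 11 rates: 120/1,920 = 6.25% and 20/960 = 2.08%, shown there as 6% and 2%.
- D10 rates: 0.40 × 0.15 = 6% and 0.20 × 0.10 = 2%.

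The figures reproduce, and they confirm that the denominator is patients referred.

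**Effect of inactive practices.** Let f be the share of intervention practices that refer nobody. This share is an assumption; the protocol gives none. Active practices keep their planned rates and all control practices stay active.

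- Referred = 40 × (1 − f) × 48
- H3 rate = [referred × 0.06] / referred = 6% for any f below 1
- Recorded quits per smoker seen = [referred × 0.06] / (40 × 200)
- Expected H1 rate = 24% × (1 − f)

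| f | Referred, intervention | H3 (intervention v control) | Recorded quits per smoker seen | H1 (intervention v control) |
|---|---|---|---|---|
| 0% | 1,920 | 6% v 2% | 1.44% v 0.24% | 24% v 12% |
| 25% | 1,440 | 6% v 2% | 1.08% v 0.24% | 18% v 12% |
| 50% | 960 | 6% v 2% | 0.72% v 0.24% | 12% v 12% |
| 75% | 480 | 6% v 2% | 0.36% v 0.24% | 6% v 12% |

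The control figure is 960 × 0.02 / 8,000 = 0.24%.

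**Practices that stop.** If half of the intervention practices stop after six months, referrals are 20 × 48 + 20 × 24 = 1,440. H3 is again 6%, and recorded quits per smoker seen are 86.4/8,000 = 1.08%. The earlier referrals stay in; only the later smokers are absent.

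**Would H3 still be significant?** The design effects are 1 + 47 × 0.017 = 1.799 and 1 + 23 × 0.017 = 1.391. Effective patients per active practice are 48/1.799 = 26.7 and 24/1.391 = 17.3. For 6% v 2%, two-sided 0.05, approximate power is 98.8%, 97.6%, 94.5% and 84.1% at f = 0%, 25%, 50% and 75%. H3 would probably succeed with most of the arm inactive.

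**The bias can also run the other way.** Suppose (illustration only) that the 24 smokers an intervention practice would have referred anyway quit at 3% instead of 2%, and the 24 extra, less ready smokers quit at 1%. Quits are 24 × 0.03 + 24 × 0.01 = 0.96, against 24 × 0.02 = 0.48 in control. H3 shows 0.96/48 = 2% v 2%, although quits per practice have doubled.

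**Check on a practice-level count.** Quits are recorded only among patients who log on and agree to follow-up. Let website users quit at the same 10% in both arms. Recorded quits per practice are 48 × 0.40 × 0.10 = 1.92 and 24 × 0.20 × 0.10 = 0.48, a fourfold ratio. The referred denominator gives 0.40 × 0.10 = 4% v 0.20 × 0.10 = 2%, twofold. A count over all smokers seen is therefore more exposed to differences in website enrolment than the present analysis.

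**The case against.** **The denominator is the hypothesis.** H3 is worded as a proportion of smokers referred, the middle column heading of Refer -> GO -> QUIT gives each link its own outcome, and Table 11 labels its primary column as those referred. This stands: the analysis may stay. What fails is the label and the statement that non-using practices are included.

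**The trial would notice abandonment.** A reader might infer that a referral system most practices give up could pass unseen. The documents do not support that. H1 uses exit cards with all smokers as denominator, independently of Refer2Quit entries. With 10 of 40 practices active it would show about 6% v 12%, a reversal. The gap is in H3 alone.

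**Practices that stop do not vanish.** Their earlier referrals stay in H3. The protocol expects some practices to use the system very little, not most to refer nobody, and the run-in and pro-active help desk work against total non-use. The shares in the table are illustrations, and the constant 6% follows from holding quitting per referral fixed.

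**The limitation is disclosed.** D9 admits that all smokers seen would be a more conservative denominator and says why it was not used. This softens the point, but the intent-to-treat label remains wrong.

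**Selection is addressed.** D9 plans to adjust for readiness to change as entered on the website. This helps only in part: the 60% (intervention) and 80% (control) of referred patients expected not to GO would have no such value.

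**The H2 precedent is not an exact match.** The secondary H2 analysis does "model the number of patients per practice who go to the website by treatment assignment", but by linear regression that also adjusts for referral rates from the exit cards. An H3 count without that adjustment would be a new analysis, not a copy.

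**Conclusion.** The concern holds as a fault of labelling and interpretation in a primary hypothesis. The H3 primary analysis conditions on referral, which follows randomisation and which the intervention is designed to raise from 12% to 24%. It is an analysis among referred patients, not intent-to-treat at practice level. The remark on the H1 denominator is also wrong against Table 10.

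Under the plan's rates the H3 contrast stays at 6% v 2% while recorded quits per smoker seen could fall fourfold, from 1.44% to 0.36%. This rests on assumed inactivity of up to 75%, 200 smokers per practice, full control activity and unchanged quitting per referral.

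Two stronger readings go too far. One is that the trial cannot detect referral failure; H1 can. The other is that quits per randomised practice should replace the current analysis as the basis for claims about assignment. Because quits are seen only in website users who agree to follow-up, that count can show 1.92 v 0.48 per practice when quitting among users is identical.

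**What to change.** 1. In D9, under Hypothesis 3, delete the intent-to-treat and all-practices wording and the remark that the denominator is that of H1. Call it an analysis among referred patients, limit its conclusion to them, and state that it is to be read alongside H1.

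2. Add a secondary or sensitivity analysis for H3: recorded six-month quits per randomised practice, with zeros kept for practices that referred nobody. Compare the arms with an offset for estimated smokers seen (patient volume × baseline or exit-card proportion of smokers), without adjusting for referral after randomisation. Table 9 already lists patients per week and the proportion who smoke. An estimate is enough for an offset, so the lack of an exact continuous count is no obstacle.

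3. State the limits of that analysis in the same paragraph. The offset is estimated and adds noise, the contrast will shrink if adoption is poor, and the count partly reflects differential website enrolment. It should not be the sole basis for a claim about the effect of assignment on cessation.

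The cost is one revised paragraph and one further model, with no new data collection.
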